The study subjects' neck and décolletage area will be divided into two equal halves. The line of division will be from the mid mental protuberance to manubriosternal junction. One half of the neck and upper chest area will be treated with ablative fractional CO2 laser while the other half will be untreated and used as a control. If desired after the study endpoint, patients may have the other side of their neck treated at no additional charge.

Primary Outcome Measures:

Physician's Global Aesthetic Improvement Scale at 12- and 24-weeks post treatment.

Photographs will be presented to a panel of independent dermatologists. The panel will be blinded to treatment parameters and the treatment laterality at each photograph time point. Each

²⁶ Ramsdell WM. Fractional carbon dioxide laser resurfacing. *Semin Plast Surg.* 2012;26(3):125-130. doi:10.1055/s-0032-1329414

²⁷ Omi T, Numano K. The Role of the CO2 Laser and Fractional CO2 Laser in Dermatology. *Laser Ther.* 2014;23(1):49-60. doi:10.5978/islsm.14-RE-01

dermatologist will be asked to identify the baseline and post-treatment images from randomized, paired images for all subjects. Reviewers will rate improvement in POC in 10% increments on a 10-point scale (0% no improvement to 100% or complete clearance)

Secondary Outcome Measures

Subject Satisfaction Assessment at 12- and 24-weeks post treatment. Subjects will assess overall satisfaction with improvement of poikiloderma of civatte using an 5-point satisfaction and aesthetic scale.

Study subjects will be followed for 24 weeks post-laser treatment to assess incidence and severity of all procedure-related adverse events.

4. Study procedures

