- Infection – patients will be counseled on signs of infection such as increased erythema, purulence, oozing and crusting. Patients will submit electronic selfies of the treatment area electronically to investigators on day 2, 3, 5, 7 and 10. Investigators will contact patients if any signs of infection are identified. For patients with skin infection within the past 6 months, topical mupirocin ointment TID applied to the nares will be prescribed to prevent staph colonization.
- Post-inflammatory hyperpigmentation: This usually happen less frequently in lighter skin types which are the groups most commonly affected by POC. However, should this occur, hydroquinone and topical retinoids can be prescribed for the patient at the study end-point to alleviate the dyschromia.
- Prolonged erythema: if erythema lasts more than 3 weeks postoperatively, a mid-potency topical steroid will be prescribed to the patient.
- Scarring: patients with personal and family history of keloid disease and hypertrophic scar formation will be excluded from the study. If hypertrophic or keloidal scars happen, intralesional steroids will be used to flatten the scars.

11. Subject Safety and Data Monitoring

All treatments will be completed at the Dermatology clinics at UT Southwestern where there are adequate resources for medical intervention in case of an adverse event such as increased bleeding, pain, or infection. The risk of severe bleeding is minimal and does not warrant the need for spare blood products or type and screening.

12. Procedures to Maintain Confidentiality

The study materials will not be disclosed to any outside persons or entities. Patient surveys collected will be stored securely in files in the dermatology offices and will not be removed from campus.

13. Potential Benefits

- Improved overall dyschromia and telangiectasia of the chest and neck area
- Overall increased patient satisfaction and quality of life
- Provide patients safe and effective alternative for treatment of discoloration and atrophy of neck and chest area which hopefully can be generalized to similar patient populations.

14. Biostatistics

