Descriptive statistics will be used to summarize patient demographics. Count (%) will be used for categorical variables; and mean, standard deviation (SD), and range (min/max) will be used to summarize continuous variables with approximately normal distributions. Skewed continuous variables will be summarized by median and interquartile range (IQR). Outcome data will be collected on patient satisfaction assessment scores and physician's global aesthetic improvement scores, as well as assessment of adverse events. The Wilcoxon signed rank test will be used to compare the magnitude of change between the baseline scores and post-intervention scores. The Wilcoxon signed rank test will also be used to compare the magnitude of change of the treated

area and the control area. A p-score of <0.05 will be considered statistically significant. The target sample size is 10 people.

Outcome Measurement:

Global Aesthetic Improvement Scale`

| | Degree | Description |
|---|-------------------------|--|
| 1 | Exceptional improvement | Excellent corrective result |
| 2 | Very improved patient | Marked improvement of the appearance, but not completely optimal |
| 3 | Improved patient | Improvement of the appearance, better compared with the initial condition, but a touch-up is advised |
| 4 | Unaltered patient | The appearance substantially remains the same compared with the original condition |
| 5 | Worsened patient | The appearance has worsened compared with the original condition |

Patient Satisfaction Assessment

| | | | | |
|--|--|--|---|--|
|  |  |  |  |  |
|  |  |  |  |  |
| Very Unsatisfied | Unsatisfied | Neutral | Satisfied | Very Satisfied |

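### The protocol does not say whether the GAIS or the blinded 0–100% photo rating is the analysed primary scale, and the percent rating has no value for worsening

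*Combined protocol and SAP*

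**What the plan says.** Section 3 (Concise summary of project), under Primary Outcome Measures, names "Physician's Global Aesthetic Improvement Scale at 12- and 24-weeks post treatment". The procedure given there is a panel of independent dermatologists, blinded to treatment parameters and to the treated side. Each "dermatologist will be asked to identify the baseline and post-treatment images from randomized, paired images for all subjects". The rating itself is then described: "Reviewers will rate improvement in POC in 10% increments on a 10-point scale (0% no improvement to 100% or complete clearance". No rule covers a pair whose order the rater gets wrong.

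Section 14 (Biostatistics) states: "Outcome data will be collected on patient satisfaction assessment scores and physician's global aesthetic improvement scores", together with adverse events. It prints a five-grade GAIS in which grade 4 is unaltered and grade 5 reads "The appearance has worsened compared with the original condition". The percent rating is not mentioned in that section. Two tests are planned: "The Wilcoxon signed rank test will be used to compare the magnitude of change between the baseline scores and post-intervention scores"; and "The Wilcoxon signed rank test will also be used to compare the magnitude of change of the treated" area with that of the control area. Neither sentence names a scale. The target is 10 people at a significance level of 0.05, with no effect size, SD, power or panel size.

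**The concern.** Two gaps combine. First, one outcome label covers two different instruments, and the reader cannot tell which supplies the numbers for the tests, or who grades the GAIS and under what masking. Second, the instrument that is described is one-sided. Nothing lies below no improvement, so worsened and unchanged sides share the bottom score even when the image order is known, although the protocol's own GAIS treats them as different outcomes.

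The stated purpose is safety as well as efficacy, and worsening is possible in the documents' own terms. Section 10 lists post-inflammatory hyperpigmentation, prolonged erythema and scarring as risks, and hyperpigmentation is part of the definition of the disease in Section 4. If the percent rating is analysed, the one blinded within-patient comparison could miss a harmful effect. It would also lose some power for a true benefit, because noise on the control side could only count as improvement.

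**Working it through.** **1. The two scales side by side.**

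| True change of a side | Percent rating (Section 3) | Printed GAIS (Section 14) |
|---|---|---|
| Improved | 10 to 100% | grades 1–3 |
| Unchanged | 0% | grade 4 |
| Worsened | 0% (inferred; no explicit rule) | grade 5 |

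**2. The plan's own figure.** The sample size of 10 cannot be reproduced, because no effect size, SD or power is given. What follows is illustration.

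**3. Assumptions.** There are 10 treated/control pairs with one score per side. Changes are Normal with the same SD on both sides, rounded to 10 points. The control mean is 0, sides are independent unless stated, and the true image order is restored. The test is the exact two-sided signed-rank test (sidedness is not stated in the plan), with mid-ranks for ties and zeros dropped. *Signed* lets worsening be negative; *floored* sets it to 0.

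**4. Smallest attainable p-value.** With m non-zero differences all in one direction, p = 2/2^m. For m = 5, p = 0.0625; for m = 6, p = 0.031. At least six are needed.

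**5. Ceiling on detecting harm.** Suppose every treated side scores 0%. A difference is then non-zero only where the control side rounds to 10% or more, with probability q = 1 − Φ(5/SD) = 0.309/0.369/0.401/0.434 for SD 10/15/20/30. Detection probability is P(Bin(10, q) ≥ 6) = **5.4/12.0/16.8/22.8%**, however large the harm. If the control sides also score 0%, it is zero.

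**6. Simulation** (8,000 or more trials per setting; error about 1 percentage point).

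| Result | SD 10 | SD 15 | SD 20 | SD 30 |
|---|---|---|---|---|
| 30-point worsening detected, signed | 100% | 96% | 79% | 46% |
| same, floored | 5% | 11% | 13% | 12% |
| 20-point worsening detected, signed | 94% | 67% | 45% | 23% |
| same, floored | 5% | 9% | 9% | 8% |
| Power for 20-point benefit, signed | 94% | 68% | 45% | 23% |
| same, floored | 92% | 60% | 38% | 18% |

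**7. Apparent size, floored** (computed exactly on the rounded scale). A 30-point mean worsening appears as a mean difference of 3.8/5.8/7.3/9.4 points against the treated side. A 20-point benefit appears as 16.2/14.7/13.7/12.5.

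**8. Correlated sides.** Two halves of one neck are unlikely to be independent. With within-patient correlation 0.5, power for the 20-point benefit is 99.7/91.9/71.9/41.2% signed and 99.0/81.5/54.7/26.2% floored. The losses are 0.7/10.4/17.2/15.0 points, or about 1 to 18 allowing for simulation error.

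**9. Several raters** (3,000 trials; half the variance between patients, half rater noise; each rating floored before averaging). For the 30-point worsening, the mean of three raters detects harm in 49/62/60/43% floored against 100/100/93/64% signed. The mean of five gives 74/84/77/54% against 100/100/95/70%. Averaging therefore recovers much of the detection, but not the apparent size in step 7.

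**10. No effect.** With equal means and equal SDs, the treated-versus-control test rejects in at most about 4% of trials. It is not inflated.

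**The case against.** The strongest reply is that the text leans towards the GAIS. It is named as primary, Biostatistics lists aesthetic improvement scores, and only the GAIS and the satisfaction scale are printed there. On that reading the analysed scale has a worsened grade and the floor does not touch the primary test. This stands as a limit on the point: the figures above apply only if the percent rating is analysed. It does not remove the point, because the percent rating is the only procedure described under the primary outcome and no sentence connects the two. The phrase about baseline scores does not settle it either, since both instruments rate change.

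Second, no figure in the documents supports a 30-point mean worsening. Section 10 says "Post-inflammatory hyperpigmentation: This usually happen less frequently in lighter skin types which are the groups most commonly affected by POC", which supports possibility rather than a group-level shift. This also stands; the 30 points are hypothetical. For a benefit, the direction the study expects, the loss with independent sides is only about 2 to 8 points.

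Third, procedure-related adverse events are followed for 24 weeks, so the study is not blind to harm. That is true, but those records do not correct the blinded side-by-side comparison.

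Two stronger readings are tempting. A reader might infer that a worsened pair whose order is misread will be scored as improvement. The protocol leaves this open but does not direct it. A reader might also infer that the before-after test will produce false improvement on a scale that cannot go negative. That requires a baseline score of 0, which the plan does not state. Neither reading is relied on here.

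**Conclusion.** The point holds in conditional form. What is firm is that the analysed primary scale is not identified, and that the only rating procedure described cannot record worsening. That a worsened side would score 0% is inferred from the floor of the scale.

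If the percent rating is analysed with one score per side, the treated-versus-control comparison can hardly show harm. Once every treated side scores 0%, detection cannot exceed 5 to 23% over the SDs considered. The power loss for a 20-point benefit is modest with independent sides and reaches about 18 points with correlation 0.5. Averaging raters reduces the loss of harm detection. These sizes rest on assumed SDs, effects and Normal changes.

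A reader might infer that the floor creates false claims of benefit. With no mean effect and equal SDs it does not. This is a cheap improvement rather than a flaw that invalidates the study; confidence is moderate.

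**What to change.** 1. State in Sections 3 and 14 which scale is the single analysed primary variable, and how the percent rating and the GAIS relate.
2. Give the blinded rating a worsening side. For each masked pair, the rater records which image looks better (no difference = 0) and by how much. The statistician then applies the image-order key: positive if the true post-treatment image was preferred, negative if the baseline image was. This also settles how misidentified pairs are scored.
3. Use these signed scores, combined across raters by a stated rule, in the within-patient treated-versus-control signed-rank test.

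If the GAIS is to be the analysed scale instead, have the panel grade it with the image order known and the treated side still masked, so that the worsened grade can be used.

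The cost is a few lines in the rater instructions and in Biostatistics, with no extra raters, visits or photographs. The drawbacks are that the rating is no longer literally percent clearance, reported improvement may look slightly less favourable, and one of the two scales becomes secondary.

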Patients with a clinical diagnosis of POC defined by a skin change with atrophy, hypopigmentation, hyperpigmentation, dilation of the fine blood vessels (telangiectasia) will be recruited. Ten patients will be consented. Before the initial visit, all patients will complete a one-month preoperative daily use of SPF 50+ sunscreen. The sun protection is to reduce further sun damage and protect skin from increased photosensitivity that may occur after laser resurfacing. At the initial visit, high resolution photographs of the affected area on the neck and décolletage area will be taken. All patients will fill out a form with demographic information. Patients will be instructed to come to their appointment with clean skin and without any lotions or moisturizers on the neck or décolletage area. Laser-specific eyewear will be provided to practitioners, patients, and all other people in the treatment room. A blue skin marking pen will be used to draw a line from mid mental protuberance to manubriosternal junction to divide tested area into two equal halves. Compounded benzocaine, lidocaine, and tetracaine (BLT) cream in a 20:8:4% concentration will be applied to the treatment area for 40 minutes prior to the procedure. Before

the treatment, topical anesthesia will be thoroughly washed off with chlorhexidine gluconate and distilled water. One pass with a 1-mm spot density and a 60micron depth will be performed followed by a 1mm spot density and a 200-micron depth will be used. The other half of the testing area will be left intact and used as the control for easy comparison. The side that undergoes treatment will be selected randomly. Forced cold air (Zimmer cooler) will also be used in conjunction with the laser device for better patient comfort.

Cold compresses with refrigerated distilled water can be used to reduce swelling and to soothe the skin with frequent reapplication of white petrolatum to keep the skin coated for days 1-5 post-procedure with strict sun avoidance for the first week post-procedure. Daily use of broad-spectrum sunscreen with SPF50+ will be required after the first week.

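### The safety outcome is filtered by judged relatedness to the procedure although two of the six listed risks overlap with the disease, and the plan does not say that adverse events are recorded by side

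*Combined protocol and SAP*

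**What the plan says.** The Introduction names safety and efficacy together as the purpose of the study. Section 3 (Secondary Outcome Measures) gives the only defined safety outcome: "Study subjects will be followed for 24 weeks post-laser treatment to assess incidence and severity of all procedure-related adverse events". Section 14 (Biostatistics) lists the outcome data to be collected and adds "as well as assessment of adverse events", with no restriction to related events and no summary measure.

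Section 4 states that patients with a clinical diagnosis defined by a "skin change with atrophy, hypopigmentation, hyperpigmentation, dilation of the fine blood vessels (telangiectasia) will be recruited". Section 10 lists six risks: ocular injury, pain, infection, post-inflammatory hyperpigmentation, prolonged erythema and scarring. Two of the entries read "Post-inflammatory hyperpigmentation: This usually happen less frequently in lighter skin types" and "Prolonged erythema: if erythema lasts more than 3 weeks postoperatively".

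On the control, Section 4 says: "The other half of the testing area will be left intact and used as the control for easy comparison". The treated side is chosen at random and the affected area is photographed before treatment. Section 14 compares treated and control areas on magnitude of change by the Wilcoxon signed rank test. It does not say whether this extends to adverse events.

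The documents give no definition of an adverse event, no causality criteria, no named assessor and no severity scale. They also give no rule for separating a new or worse sign from disease present at baseline.

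**The concern.** Under the Section 3 wording, a judgement of relatedness decides which events enter the numerator. For pain, infection, ocular injury or a hypertrophic scar, that judgement is usually straightforward. For brown or red skin on the neck at week 12 or 24 it is not, because the disease produces the same signs. Section 2 describes erythema and dyschromia as features of POC that improved under another laser. It also says that existing treatments may cause hypopigmentation and post-inflammatory hyperpigmentation.

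Persisting disease on the treated half could therefore be counted as a laser event, and a true laser-induced pigment change could be put down to the disease. A half that shares the patient's season, sun protection and disease course is available as a reference, but the plan does not say that it will be used for this. If signs on the control half are not recorded during the study, the comparison may be impossible to reconstruct reliably afterwards.

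The efficacy ratings do not fill the gap. The panel's percentage scale starts at no improvement and so cannot record worsening. The Global Aesthetic Improvement Scale has a worsened grade, but it is global and does not say which sign worsened.

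**Working it through.** The plan states no adverse event rate, so there is no figure to reproduce. The only numerical input from the documents is n = 10 (Sections 4 and 14). All event rates and error rates below are assumptions.

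**Overlap with the disease.** Of the six risks in Section 10, hyperpigmentation and erythema match features of POC. Ocular injury, pain, infection (which has its own signs) and hypertrophic or keloidal scarring do not. That is 2 of 6. The documents neither rank these risks nor give frequencies.

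**Weight of one patient.** 1/10 = 10 percentage points.

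**Effect of misattribution.** Let p be the true incidence, *sens* the share of true events counted, and *spec* the share of event-free patients correctly not counted. Expected reported incidence = sens × p + (1 − spec) × (1 − p).

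| Assumed error | p = 10% | p = 20% | p = 30% |
|---|---|---|---|
| Half of true events put down to POC (sens 0.5, spec 1) | 5% | 0.5 × 0.20 = 10% | 15% |
| POC counted as an event in 20% of event-free patients (sens 1, spec 0.8) | 28% | 0.20 + 0.2 × 0.80 = 36% | 44% |

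The error can go either way. Nothing in the documents says which of these patterns, if either, would occur.

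**Precision, kept separate from bias.** Exact (Clopper-Pearson) 95% intervals at n = 10 are 0 to 30.8% for 0 events, 0.3 to 44.5% for 1 event and 2.5 to 55.6% for 2 events. These widths come from the sample size and would be the same under perfect attribution.

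**What recording both halves would give.** Assume a laser-caused risk of 20% and an independent background risk of 10% per half. The treated half then shows 1 − 0.8 × 0.9 = 28%, the control half 10%, and the difference is 18 points. With background 20%, the figures are 1 − 0.8 × 0.8 = 36% against 20%, a difference of 16 points. The contrast stays close to the laser-caused risk with no judgement of cause.

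**What it would not give.** In an exact McNemar test with d discordant patients, all in one direction, two-sided p = 2 × 0.5^d. For d = 5, p = 0.0625; for d = 6, p = 0.031. At least 6 of the 10 patients must therefore be discordant, all one way, for p < 0.05. With no control-only events, power is 0.6%, 4.7% and 37.7% for assumed treated-only rates of 20%, 30% and 50%. The comparison can only be descriptive.

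**The case against.** The strongest reply is that the design already makes confusion unlikely. The laser is confined to one side of a marked midline and baseline photographs exist, so a new one-sided sign should be recognizable. Background change from sun is limited by the sunscreen and sun-avoidance requirements and the undertaking not to tan, and Section 2 describes the disease as chronic. Section 10 gives prolonged erythema a time threshold. Section 14 does not restrict adverse events, and Section 4 has patients report any concern through MyChart. For a 10-patient study, what is missing might be no more than a reporting detail.

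Much of this stands as mitigation, but none of it is an attribution rule, and no section requires the photographs or the other half to be used in assessing events.

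Several stronger readings are tempting and are not supported:

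- A reader might infer that the main expected events all look like POC. Only two of the six listed risks do, and the documents do not rank them.
- A reader might infer that the untreated half is reserved for efficacy. The plan calls it the control without limiting its use; on adverse events it is silent.
- A reader might infer that relatedness will be decided by someone who knows the treated side. Blinding is described only for the photograph panel, but no section names the adverse event assessor.
- A reader might take the wide exact intervals as the size of the defect. They reflect n = 10.

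It is also fair that scoring every early selfie would count ordinary post-laser redness as an event and swamp the comparison. The fix avoids this.

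**Conclusion.** The point holds in limited form and should be addressed. The defined safety outcome depends on a relatedness judgement for which the plan gives no criteria, two listed risks overlap with the disease, and Sections 3 and 14 differ on which events count. Reported incidence could be too high or too low by 10 percentage points for each misclassified patient. The illustrative shifts, from 20% to 10% or to 36%, rest wholly on assumed error rates and are not estimates for this trial.

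A reader might also infer that the control half would settle attribution. It would not. It informs the question by showing what happens on untreated skin over the same weeks, but at n = 10 a formal paired comparison has almost no power at modest event rates. Knowledge of the treated side could still influence an assessor who is not blinded. The gain is a count that no longer depends on judged cause, obtained from visits and photographs already planned.

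**What to change.** 1. Reconcile Section 3 with Section 14 on whether all adverse events or only procedure-related ones are collected and reported. State the assessor, the causality criteria and the severity scale.
2. At the existing week 12 and 24 visits, complete the same short checklist for each half: darker or lighter pigment, erythema, texture change or scarring. Record any sign that is new or worse than that half's own baseline photograph, whatever its presumed cause. Put investigator-judged relatedness in a separate column.
3. Report patient counts and severity for treated and control halves side by side, with exact intervals. State in Section 14 that this is descriptive.
4. Keep the early MyChart selfies for detecting complications and leave them out of the by-half comparison, so that expected early redness is not counted as an event. The selfie days in Sections 4 and 8 differ from those in Section 10 and need separate reconciliation.

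The cost is one extra checklist per visit, or 10 patients × 2 visits = 20 in all with full attendance, and one descriptive table of limited precision. No new visits, procedures or staff are needed.
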